**11/06/2024**

## **1. Study protocol**

### **1.1. Expected duration of participation of individuals**

All participants (n=216) will be invited to a 45-minute visit (test). A second visit will be organized for the 60 patients randomly selected for a 15-day retest.

The maximum duration of participation is therefore 15 days.

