## **2. Statistical analysis plan**

### **2.1. Data Analysis Method**

### 2.1.1. General

The statistical analysis will be carried out with the Stata software (version 15, StataCorp, College Station), considering a first-kind bilateral risk of error of 5%.

The sample will be described by associated numbers and percentages for categorical variables and by mean and standard deviation or median and interquartile range for quantitative variables, with respect to their statistical distribution. Normality will be studied by the Shapiro-Wilk test and/or histogram. Graphical representations will be associated with the analyses as much as possible.

Patients will be described and compared between groups at baseline according to the following variables: compliance with eligibility criteria, epidemiological characteristics and clinical characteristics.

A description of the deviations from the protocol, the patients distributed according to these deviations and the causes of abandonment will also be carried out.

The initial comparability of the two arms will be assessed on the main characteristics of the participants and potential factors associated with the primary outcome. Any difference between the two groups on one of these characteristics will be determined according to clinical considerations and not just statistical ones. Comparisons between groups will be made systematically (1) without adjustment and (2) by adjusting for factors whose distribution could be unbalanced between groups despite the matching.

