Internal **structure validity** explores the coherence of the internal layout of the questionnaire. This validity will be evaluated by studying the following parameters: for items of a categorical nature: proportion of patients for each of the modalities of each item ('difficulty', denoted  $p$ ), variance of each item (denoted  $p(1-p)$ ), 'item-score' correlations (so-called biserial point correlation coefficient, i.e. correlation between a dichotomous variable and a quantitative variable) and multi-trait matrix of correlation coefficients (inter-item and item-dimension) for the items of a quantitative nature.

A factor analysis will allow us to study the relationships between the modalities of each of the items.

These analyses will be complemented by an item response theory approach; specifically, a Rasch model analysis will be implemented to study the internal structure of the AHS, taking into account inter and intra item variability. The following indicators will be calculated, among others: one-dimensionality, item difficult, DIF (Differential Item Functioning), reliability alpha (PSI: person separation index), fit (overall, outfit, infit).

The DHEQ-fr scores of patients in the HD group will be compared to those of the "control" group by Student's t-test or Mann-Whitney test if the conditions for the application of the t-test are not met. Homoscedasticity will be studied by Fisher-Snedecor test. Results will be expressed in terms of effect sizes and 95% confidence intervals.

The study of the relationships between variables of a quantitative nature (DHEQ-fr, GOHAI, OHIP-49 and 14) will be analyzed by estimation of correlation coefficients (Pearson or Spearman, with regard to the statistical distribution).

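### Unequal variances between HD and control send the DHEQ-fr comparison to Mann-Whitney, which does not correct for them; no unequal-variance t-test is offered and the effect size is unnamed

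*Protocol*

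**What the plan says.** Section 2.1.2 of the protocol compares DHEQ-fr scores between the HD and control groups by "Student's t-test or Mann-Whitney test if the conditions for the application of the t-test are not met". The next sentence adds: "Homoscedasticity will be studied by Fisher-Snedecor test". Section 2.1.1 gives the other check: "Normality will be studied by the Shapiro-Wilk test and/or histogram". No threshold is stated for either check, and no t-test for unequal variances is mentioned.

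On reporting, section 2.1.2 says: "Results will be expressed in terms of effect sizes and 95% confidence intervals". It does not name the effect size, tie it to one of the two tests, or say whether a mean difference is the target.

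Section 2.1.1 also asks for each group comparison both unadjusted and "by adjusting for factors whose distribution could be unbalanced between groups despite the matching". It sets a two-sided 5% level. Section 1.1 gives 216 participants in total; the text at hand does not say how they divide between HD and control.

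**The concern.** The protocol makes the test depend on the data. Because equal variance is one of the t-test conditions and is explicitly checked, the plain reading is that unequal variances lead to Mann-Whitney. That is the wrong destination. The null standard error of Mann-Whitney assumes identical distributions, so it is miscalibrated when spreads or shapes differ. The usual answer to unequal variances, the Welch t-test, is absent.

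Unequal spread or shape is plausible here. Controls are confirmed free of HD, yet they complete an HD-specific questionnaire, so they may score near the floor. That is an inference; the protocol gives no DHEQ-fr mean, SD or distribution.

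At stake is mainly the reported estimate. With the effect size unnamed, it may change with the test, and a rank-based quantity differs from a mean difference when shapes differ.

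**Working it through.** The protocol has no figure to reproduce on this point: 216 comes without an effect size, SD, power or group split. The checks use N = 216 and a two-sided 5% level. Splits, SDs and shapes are assumed. Simulations used 4,000 runs per scenario unless noted (standard error √(0.05 × 0.95 / 4000) ≈ 0.35 points at a 5% rate).

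**1. The variance check on skewed scores.** With equal variances and the same shape in both groups, the log variance ratio has about (1 + excess kurtosis / 2) times the variance that the F test assumes. A gamma score with shape k has skewness 2/√k and excess kurtosis 6/k, so the factor is 1 + 3/k. The large-sample rejection rate is 2[1 − Φ(1.96/√factor)].

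| Shape k | Skewness | Factor | 1.96/√factor | Formula | Simulated, 108/108 |
|---|---|---|---|---|---|
| 4 | 1.0 | 1.75 | 1.482 | 13.8% | 13% |
| 2 | 1.4 | 2.50 | 1.240 | 21.5% | 20% |
| 1 | 2.0 | 4.00 | 0.980 | 32.7% | 31% |

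**2. Where unequal variances are sent.** Take normal scores with equal means, SD 1 in the first group (size m) and SD 2 in the second (size n).

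For Mann-Whitney, the variance of the estimated P(X > Y) is about v1/m + v2/n, with v1 = arcsin(0.2)/2π = 0.0320 and v2 = arcsin(0.8)/2π = 0.1476. The test assumes (1/m + 1/n)/12. Let R be the true variance over the assumed one; the rejection rate is 2[1 − Φ(1.96/√R)].

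- 108:108: R = 0.001663/0.001543 = 1.078, giving 5.9%
- 162:54: R = 0.002931/0.002058 = 1.424, giving 10.1%
- 54:162: R = 0.001504/0.002058 = 0.731, giving 2.2%

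For the pooled t-test, R = (1/m + 4/n) / {[(m + 4n)/(m + n)](1/m + 1/n)}, which is 1.00, 1.857 and 0.538, giving 5.0%, 15.0% and 0.8%.

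| Split | Mann-Whitney, simulated | Pooled t, simulated | Welch, simulated |
|---|---|---|---|
| 108:108 | 6.3% | 5.0% | 4.9% |
| 162:54 | 9.7% to 10.6% (two runs) | 15.2% | 5.3% |
| 54:162 | 1.9% to 2.6% (two runs) | 0.7% | 4.7% |

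Mann-Whitney is less distorted than the pooled t-test at unequal sizes, but it does not restore 5%. Welch does. The error goes up or down according to which group is larger.

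**3. Different shapes.** The rule was read as Mann-Whitney if the F test or either group's Shapiro-Wilk test has p < 0.05. Means are equal.

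- Same skewed shape and SD in both groups: Mann-Whitney 4.4% to 5.1%, Student 4.6% to 5.3%. Both are valid.
- HD normal, controls exponential, equal SDs: Mann-Whitney 11.4% to 16.6% across the splits, Welch 4.5% to 5.5%. The mean difference is 0, while the Hodges-Lehmann shift is 0.12 SD and P(HD > control) is 0.538.
- HD normal with SD 1.5, controls exponential with SD 1: Mann-Whitney 9.2% at 108:108 and 4.1% to 10.6% across the splits, Welch 4.5% to 5.3%.

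**4. Conditions actually met.** Three independent 5% checks would still switch in 1 − 0.95³ = 14.3% of samples. This is harmless to the level: 4.7% to 6.1% under the rule against 4.6% to 6.0% for Student throughout.

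**5. The estimate, if a rank-based shift interval were reported.** With true mean difference 1, controls gamma with SD 0.7, HD normal with SD 1 and 108/108, the Hodges-Lehmann 95% interval covers the mean difference in 93.8%, 92.7% and 90.9% for shapes 4, 2 and 1, against 94.5% to 94.9% for Welch. Allowing for run-to-run variation, that is about 90% to 94% against about 95%. With SD 1 for HD and 0.5 for controls (shape 2), it covers 90.6% at 72 HD/144 controls but 96.2% at 144/72.

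**6. Practical weight.** For an assumed true difference of 0.8 SD, t-test power with 216 participants exceeds 99.9% at 1:1 and at 2:1.

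**The case against.** The best counter-argument is that this is a conventional rule on one of many validity checks, and that several stronger readings go beyond the text.

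- A reader might infer that the reported interval will fail to describe the mean score difference. The protocol promises neither a mean difference nor a Hodges-Lehmann interval, and a standardised mean difference can accompany either test. The supportable criticism is that the measure is unnamed. In the 108/108 runs the rank interval covered its own target, the median pairwise difference, in 94.2% to 94.8%.
- A reader might infer that Mann-Whitney fails for skewed scores in general. It does not when both groups share one skewed shape. A false alarm from the variance check in that setting therefore leads to a valid test, which limits what step 1 shows on its own.
- A reader might call the switch nearly certain. That needs assumed floor scores and an automatic threshold. The protocol gives no score distribution, and normality may be judged from a histogram.
- A reader might say the adjusted and unadjusted results will be on incompatible scales. The adjusted model is not specified, so this is only a risk.
- A separate analysis plan could name the effect measure.

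All of this stands, and it narrows the point. It does not remove the rule itself, which the protocol states: failed t-test conditions, variance included, lead to Mann-Whitney, with no unequal-variance alternative.

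**Conclusion.** The point holds in a limited form. As a test of means at unequal spreads, the stated route rejects between about 2% and 10% instead of 5% in the normal SD 1 v 2 scenarios, depending on the split. It reaches up to 16.6% when only one group is skewed. Welch stays near 5% in these scenarios. If the effect size followed the test, coverage of the mean difference would fall by about 1 to 5 points at 108/108 with SD 0.7 v 1, and could err in either direction at unequal sizes.

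These sizes rest on assumed splits, SDs and shapes, on floor-type control scores for the skewed cases, and on a 5% threshold for each check where the whole rule was simulated. The documents do not support the claim that the confidence interval will be wrong, nor that the known-groups conclusion is in doubt; with a large difference it would rarely change. This is a cheap improvement of modest practical weight.

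**What to change.** Drop the Fisher-Snedecor check as a gate for this comparison, and do not let the normality check choose the test either. Specify in advance:

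- the Welch mean difference with its 95% CI, in all cases;
- one named standardised effect size, with its SD convention stated so that equal SDs are not assumed;
- for the adjusted comparison in section 2.1.1, a linear model with robust standard errors, so that adjusted and unadjusted results are on the same scale;
- Mann-Whitney as a supportive analysis, reported as a probability of superiority.

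The cost is a few sentences in the plan, with the same data and software. The downside is a negligible loss of power if the variances are in fact equal.

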#### *2.1.3. Method of accounting for missing, unused or invalid data*

A sensitivity analysis will be conducted to measure the impact of missing data and determine the most appropriate imputation method. Complete and missing samples will be compared for key socio-demographic and clinical characteristics, as will test and retest samples.

Additional analyses will then be carried out according to the statistical nature of the missing data (missing at random or not).

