#### **Visit 2 (Retest)**

#### **HD Group and Control**

- Self-administration of DHEQ-fr questionnaires.

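### The planned comparison of test and retest samples is nested and says little about selective non-return; returned versus not returned among the 60 drawn would be a better contrast

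*Protocol*

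**What the plan says.** Protocol section 1.1 has all 216 participants attend the test visit, and then: "A second visit will be organized for the 60 patients randomly selected for a 15-day retest". The retest group is therefore a random subset of the test group. At Visit 2 the only act listed, for both groups, is "Self-administration of DHEQ-fr questionnaires" (section 1.2), so any comparison of samples has to use Visit 1 characteristics.

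Section 2.1.3, on missing, unused or invalid data, says: "Complete and missing samples will be compared for key socio-demographic and clinical characteristics, as will test and retest samples". It does not define the four samples it names, and it does not say which question the test/retest comparison is meant to answer. No expected loss at retest is given. Section 2.1.1 sets a two-sided 5% level and adds that a description of deviations and "the causes of abandonment will also be carried out".

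**The concern.** The draw is random, so apart from chance the retested patients can be unrepresentative only because some drawn patients fail to return. The informative contrast is therefore within the 60, between those who completed the retest and those who did not. Setting the retest sample against the test sample has two weaknesses for that purpose. Every retested patient is counted on both sides, and about 216 − 60 = 156 people who were never asked back, and so carry no information about who returns, are added to one side.

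Test-retest reproducibility is one of the two fidelity criteria in section 2.1.2. It is judged by kappa, Lin's coefficient and correlation, all of which depend on the spread of scores among those retested. A check that rarely signals could be cited as showing comparable samples when it had little chance of showing anything else.

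**Working it through.** **Inputs from the protocol.** Test sample 216 and retest draw 60 (section 1.1); two-sided 5% level (section 2.1.1). The protocol states no power or expected loss for this check, so there is no figure to reproduce.

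**Assumptions, not in the protocol.** A fraction *m* of the 60 does not return. Non-returners differ from returners by *d* within-group SDs on one Visit 1 characteristic. The comparison is an ordinary two-sample t-test, since section 2.1.3 names no test.

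**1. False-positive rate with no loss and no bias (60 against 216, overlapping).**
- Standard error the test assumes: √(1/60 + 1/216) = 0.146.
- Actual standard error: (1 − 60/216) × √(1/60 + 1/156) = 0.110.
- Ratio: 0.752.
- Actual size: 2 × [1 − Φ(1.96/0.752)] = 0.009, that is 0.9% instead of 5%.

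**2. Size of the contrast.** Returned minus not returned has expectation *d*. Retest minus test has expectation *m × d*, because the test sample contains non-returner types in proportion *m*. With 12 of 60 lost and *d* = 0.8, the contrast shrinks from 0.8 to 0.2 × 0.8 = 0.16 SD.

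**3. Power at 12 of 60 and *d* = 0.8, normal approximation.**
- Direct (48 against 12): SE = √(1/48 + 1/12) = 0.323; power = Φ(0.8/0.323 − 1.96) = 70%.
- Nested (48 against 216), ignoring the overlap: SE = √(1/48 + 1/216) = 0.160; power = Φ(0.16/0.160 − 1.96) = 17%. Allowing for the overlap lowers this to about 10% (simulated, next step).

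**4. Simulated detection rates (6,000 runs per case, two-sided 5%).**

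| Not returned | *d* (SD) | Nested: returners vs all 216 | Returners vs all other tested patients | Returned vs not returned |
|---|---|---|---|---|
| 6 of 60 | 0.5 | 2% | 7% | 21% |
| 6 of 60 | 0.8 | 3% | 10% | 45% |
| 12 of 60 | 0.5 | 5% | 11% | 33% |
| 12 of 60 | 0.8 | 10% | 21% | 69% |
| 18 of 60 | 0.5 | 8% | 17% | 42% |
| 18 of 60 | 0.8 | 21% | 36% | 80% |

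In the most extreme case run (24 of 60, 1.0 SD) the nested check reaches 51%, against 96% for the direct one.

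The fourth column separates the two causes. At 12 of 60 and 0.8 SD, removing the overlap raises detection from 10% to 21%; leaving out the uninvited patients raises it from 21% to 69%. Dilution, not overlap, is the main cause.

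**5. Effect on the retest coefficient in a severe case.** Take 20% loss, a 1 SD gap in Visit 1 score, unit variance within returners and within non-returners, and an assumed reliability of 0.80 in all 60.
- Total variance: 1 + 0.2 × 0.8 × 1² = 1.16.
- Error variance: 0.20 × 1.16 = 0.232.
- Reliability in returners: 1 − 0.232 = 0.77, a shift of about 0.03.
- The same steps give a shift of about 0.02 from 0.90 and about 0.05 from 0.70.
- For comparison, sampling error with 48 patients at 0.80: SE ≈ (1 − 0.64)/√47 = 0.053, or about ±0.10.

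**The case against.** A reader might infer that the protocol never compares returners with non-returners. The text does not support that. The first half of the sentence in section 2.1.3 compares complete with missing samples, and a drawn patient without a retest has missing data. What stands is only that the clause is undefined: it could equally mean patients with missing items, or even count the patients never invited as lacking a retest.

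A reader might also infer that test versus retest is the protocol's check on loss. No such purpose is stated. It may be meant to show that the random 60 resemble the 216, which is a fair question because a random draw can differ by chance. Even then, drawn versus not drawn is the clean contrast, and the nested one has the wrong error rate.

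The detection rates rest on a procedure the protocol does not specify. It names no test, and the comparison could be run as retested against not retested. That would remove the overlap but, as the fourth column of the table shows, most of the loss of power would remain.

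Other provisions also bear on loss: the reasons for abandonment are described, and section 2.1.3 adds a sensitivity analysis and further work according to the missing-data mechanism. Reasons for leaving are not a comparison of characteristics, but this check is not the only safeguard.

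Finally, the direct comparison is itself weak for moderate selection (21% to 42% at 0.5 SD for 6 to 18 lost), and the shift in step 5 is smaller than the coefficient's own sampling error. Both objections stand, and they limit how much is at stake.

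**Conclusion.** The point holds as a minor one. As worded, test versus retest is a comparison of a sample with a subset of itself. Its true false-positive rate with full return is about 1%, and its power against selective non-return is about 2% to 21% where the direct contrast has about 21% to 80%. Those ranges assume 6 to 18 of 60 not returning, a gap of 0.5 to 0.8 SD and an ordinary t-test; the protocol gives none of these. If everyone drawn returns, there is no such bias to detect.

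It would go too far to conclude that the reproducibility results are likely to be materially wrong. Who would fail to return is not documented, and even the severe case above moves a reliability of 0.80 only to about 0.77. What is at stake is the soundness of a comparability statement, not the main retest result.

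**What to change.** In section 2.1.3, replace the comparison of test and retest samples by two comparisons without overlap:

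1. Among the 60 drawn, retest completed versus not completed, on Visit 1 characteristics: group, DHEQ-fr score, socio-demographic variables and, for HD patients, the Schiff and EVA scores. Report differences with 95% confidence intervals, not p-values alone.
2. Drawn versus not drawn, as a check that the random 60 represent the 216.

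Add that, if the first comparison shows a difference, the retest coefficients are reported as applying to patients who returned. State also whether the complete and missing samples include drawn patients without a retest.

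This is a cheap improvement: a sentence or two and a record of who was drawn, with no new patient data. The downside is that the non-returner group will be small, so its intervals will be wide.

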#### *2.1.4. Interim analyses*

An intermediate analysis will be carried out as part of a Master II thesis. Inclusions will be continued during this period as there is no risk to participants.
